According to clinical guidelines, when conducting thrombolytic therapy with Fortelyzin® in the intensive care unit, it is necessary to ensure that the following vital signs are monitored for at least 24 hours:

- * blood pressure;
- * heart rate;
- * frequency of respiratory movements;
- * body temperature;
- * oxygen saturation.

During thrombolytic therapy and within 24 h after its completion, it is necessary to monitor the dynamics of neurological status.

Drug-Drug Interactions

Fertilyzin® should not be administered concurrently with other medications. If severe bleeding occurs (especially from non-compressible vessels), the administration of the thrombolytic should be stopped, and fresh frozen plasma should be administered.

Due to the possible development of arterial hypertension observed during thrombolysis with Actilyse®, according to clinical guidelines antihypertensive drugs can be used in dosage forms for intravenous administration:

- * angiotensin-converting enzyme inhibitors -enalaprilate (Enap R); however, simultaneous use of angiotensin-converting enzyme inhibitors with alteplase increases the risk of angioedema;
- * nitrates – isosorbite dinitrate (isoket), nitroglycerin; however, the frequent side effect of nitrates is headache, which can mask the development of intracranial hemorrhage;
- * vasodilators – sodium nitroprusside;
- * ganglioblockers-azamethonium bromide (Pentamine);
- * alpha-blockers-urapidil (Ebrantil), proxodolol (Albetor);
- * calcium channel blockers - nimodipine (Nimotop).

Side effect/Adverse events

Bleeding of varying severity is possible. Bleeding events associated with thrombolytic therapy can be divided into two large groups:

- external bleeding (usually occurred at the sites of blood vessel punctures);
- internal bleeding in any part or cavity of the body.

The possibility of allergic reactions is not excluded.

As a rule, therapeutic doses of Fortelyzin® do not lead to arterial hypotension, but the possibility of its occurrence cannot be excluded.

Experience of using Fortelyzin® in AMI patients with simultaneous use of anticoagulant and dual antithrombotic therapy showed a minimal percentage of hemorrhagic stroke (0.46 %) or major bleeding requiring blood transfusion (1.6%).

However, due to the short half-life of Fortelyzin® and its minimal effect on the blood coagulation system (drop in fibrinogen is less than 10 %), no clotting factor replacement is required.

In the case of bleeding, accompanied by a decrease in hemoglobin by more than 3 g/dl, the use of blood components transfusion is required.

Bleeding that occurs within the first 24 hours after Fortelyzin® administration can be regarded as associated with drug use.

Hemorrhagic transformation of the brain lesion is symptomatic if its development leads to an increase in the total NIHSS score by 4 points or more. In most cases of intracerebral hemorrhages, asymptomatic hemorrhagic transformation is registered after thrombolytic therapy. It is detected by CT or MRI and often accompanied by clinical improvement and is evidence of reperfusion.

If intracerebral hemorrhage is suspected, neuroimaging (brain CT or MRI) must be performed. If necessary, the patient should be consulted by a neurosurgeon.

Overdose (intoxication)

Adverse drug effects from overdose can result in hemorrhagic complications.

In the case of local bleeding – it can be stopped without stopping the drug administration.

CLINICAL TRIAL PROTOCOL

If life-threatening bleeding occurs, Fortelyzin® administration should be stopped and fresh frozen plasma or whole blood should be prescribed. If necessary, to neutralize the effect of Fortelyzin®, an anti-fibrinolytic agent can be administered, for example, aminocaproic acid, or tranexamic acid.

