After enrollment, patients will be randomized using the "envelope method" into two equal groups of 168 patients each (a total of 336 people, including 10% who may have dropped out) and assigned to receive either Fortelyzin® or Actilyse®. Fortelyzin® will be given as single i.v. bolus over 5 - 10 seconds. Actilyse® will be administered following the instruction for use.

To compare the efficacy and safety of Fortelyzin® vs Actilyse®, patients will be monitored for 90 days after administration of the drug. During this period, patients will have 6 visits (Table 5).

Table 5. Plan of the trial

	V 1	V 2	V 3	V 4	V 5	V 6
	0	1 day	2 days	7 days	14 days	90 days
Signing Informed consent	+	–	–	–	–	–
Demographic data	+	–	–	–	–	–
Previous treatment	+	–	–	–	–	–
CT/MRI SCAN	+	+	–	+	–	–
ASPECTS	+	+	–	+	–	–
Dynamics of neurological status	–	+	+	–	–	–
Changes by organs and systems	–	+	+	+	+	–
TOAST criteria	–	–	+	–	–	–
Medical history	+	–	–	–	–	–
Measurement of vital signs	+	+	+	+	+	+
Physical examination	+	–	–	–	–	–
Concomitant diseases	+	–	–	–	–	+
NIHSS	+	+	+	+	+	+
Bartel	–	–	–	+	+	+
Rankin	+	–	+	+	+	+
Meningeal symptoms	+	+	+	+	+	–
ECG	+	–	–	+	+	–
Duplex scanning of the major arteries of the head (if necessary)	+	–	–	+	–	–
Coagulogram	+	+	+	+	+	–
Complete blood count	+	–	+	+	+	–
Biochemical blood analysis	+	–	–	+	+	–
Blood sampling for Pharmacokinetic analysis	–	+	–	–	–	–
Common urine analysis	+	–	+	+	+	–
Inclusion/Exclusion criteria	+	–	–	–	–	–
Angiography of cerebral vessels (if necessary)	+	–	–	–	–	–
Administration of Fortelyzin® or Actilyse®	–	+	–	–	–	–
Change in concomitant therapy	–	+	+	+	+	+
Registration of AE	–	+	+	+	+	+
Bleeding assessment	–	+	+	+	+	–

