The individual identification code assigned to the patient is not subject to change.

The Investigator should maintain a separate Identification Registry containing the individual numbers, surnames, dates of birth, addresses, phone numbers, and medical records (if available). Only the initials, dates of birth, and unique patient numbers that are part of the Individual Patient Identification Code will be used in the report and trial documentation.

The randomization plan will be known by the Principal Investigator and Regulatory Authorities.

Visit 2.

- Administration of Fortelyzin® or Actilyse®.
- On Visit 2, the changes in neurological status will be recorded, as well as registration and evaluation of bleeding and adverse events based on patient complaints, data from neurological, physical, and laboratory-instrumental studies.

Table 7. Monitoring of parameters at the moment of thrombolysis

Trial parameter	Frequency of examination
BP	Every 15 minutes to 2 hours after the start of thrombolysis
Vital signs	Every 30 minutes for 6 hours
NIHSS	Every 15 minutes for 1 hour
Meningeal symptoms	Every 15 minutes for 1 hour

Table 8. Monitoring of parameters during the first day (24h) after thrombolysis

Trial parameter	Frequency of examination
BP	Every hour until the end of the day (within 24 hours)
Vital signs	Every 30 minutes to 6 hours, then every hour until the end of the day
Meningeal symptoms	Every hour for 24 hours
NIHSS	Every hour for 24 hours

- CT/MRI 24 hours after TLT or if the patient's condition worsens
- assessment of CT changes according to ASPECTS
- registration of adverse events (AE)
- assessment of bleeding

All adverse events identified should be recorded in the Case Report Form (CRF). The Investigator should report the adverse events to Roszdravnadzor within the next 24 hours. The assessment of bleeding is carried out according to the corresponding scales (see Safety assessment). Monitoring of coagulogram parameters (fibrinogen) will be carried out within 24 h from the time of Fortelyzin® or Actilyse®

administration. CT/MRI examination of the brain will be repeated 24 hours after the thrombolysis or if the patient's condition worsens.

During the visit, patients will receive treatment in accordance with the Russian Clinical Guidelines for Thrombolytic Therapy in Ischemic Stroke, 2015.

Visit 3.

- verification of the stroke subtype according to TOAST criteria
- measurement of vital signs
- physical examination

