9.1.6. Complete and biochemical blood analysis

The tests are carried out in accordance with the methodology adopted in the clinical center laboratory. The following parameters will be measured:

- complete blood count (number of red blood cells, white blood cells, platelets, hemoglobin, hematocrit, leukocyte formula, ESR)
- biochemical blood parameters (glucose, ALT, AST, bilirubin, creatinine, total protein, sodium, potassium, CK, urea, cholesterol, HDL-C, triglycerides)
- coagulogram (fibrinogen, INR, APTT, prothrombin index)

In the case of clinically significant abnormalities, these phenomena are recorded as a concomitant disease (during the screening) or as an adverse event (during the trial).

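### No blood count is scheduled in the first 24 hours after dosing, so an early hemoglobin fall may be recognized late, left undated or masked

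*Combined protocol and SAP*

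**What the plan says.** Section 2 (Side effect/Adverse events) contains two statements that bear on early bleeding. The first uses a hemoglobin threshold: "In the case of bleeding, accompanied by a decrease in hemoglobin by more than 3 g/dl, the use of blood components transfusion is required". The second defines an attribution window: "Bleeding that occurs within the first 24 hours after Fortelyzin® administration can be regarded as associated with drug use".

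Table 5 in section 8 places the six visits at "0 1 day 2 days 7 days 14 days 90 days". Its row "Complete blood count" is marked at V1, V3, V4 and V5, and not at V2 or V6. Its row "Bleeding assessment" is marked at V2 to V5. Administration of the drug and a coagulogram are also marked at V2.

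The Visit 2 text in section 9 calls for "registration and evaluation of bleeding and adverse events based on patient complaints, data from neurological, physical, and laboratory-instrumental studies". The one safety blood test it names is the coagulogram: "Monitoring of coagulogram parameters (fibrinogen) will be carried out within 24 h". Hemoglobin belongs to a different test, as section 9.1.6 shows: "complete blood count (number of red blood cells, white blood cells, platelets, hemoglobin, hematocrit, leukocyte formula, ESR".

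Section 12 requires every bleed to be recorded in the CRF and classified on both the GUSTO and TIMI scales. The top grade on either scale makes the bleed a serious adverse event.

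**The concern.** Bleeding is the main risk that section 3 names for the study drug, and the first 24 hours are the period that section 2 singles out for attribution. In that period the plan asks staff to evaluate bleeding partly on laboratory data, but schedules no test that measures blood loss. Fibrinogen is not a substitute. It also moves with the assigned treatment: in the phase III infarction study described in section 2, the maximum first-day drop was 38% after Actilyse and 7% after Fortelyzin.

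What is at stake is the quality and comparability of the early bleeding data. The trial is open-label. If a first-day hemoglobin exists only when someone chooses to order it, the choice may depend on knowing which drug was given. The between-arm comparison of bleeding would then rest partly on unequal ascertainment.

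**Working it through.** The point turns on the schedule, not on a calculation. The plan gives no figure to reproduce, so the relevant places are set side by side.

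| Item | V1 (0) | V2 (1 day) | V3 (2 days) | V4 (7 days) | V5 (14 days) | V6 (90 days) |
|---|---|---|---|---|---|---|
| Drug given | – | + | – | – | – | – |
| Bleeding assessment | – | + | + | + | + | – |
| Coagulogram | + | + | + | + | + | – |
| Complete blood count | + | – | + | + | + | – |

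1. **Is the gap only a slip in the table?** No. The Visit 3 list in section 9 includes a complete blood count and the Visit 2 text does not, so table and text agree. V2 is the only visit with a bleeding assessment but no blood count.

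2. **Does V2 cover the attribution window?** Yes. Tables 7 and 8 in section 9 place dosing and the following 24 hours within Visit 2, and Visit 3 comes after them. Scheduled post-dose counts inside the window: 0. Scheduled post-dose counts in all: 3 (V3, V4 and V5).

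3. **How late is the first one?** Read literally, V3 is 2 days, or 48 hours, after dosing. That is 48 − 24 = 24 hours after the window closes. The V2 column headed 1 day contains the dosing itself, so if that is the dosing day, V3 could fall soon after 24 hours. The documents do not settle this.

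4. **What can the V3 count show?** Compared with V1, it can still reveal a fall caused by a first-day bleed. It cannot say when the fall happened. Section 10 (Permitted concomitant therapy) allows antiplatelet agents and anticoagulants once 24 hours have passed and imaging has excluded intracranial bleeding. A fall seen at V3 may therefore come from the thrombolytic or from drugs started after it. If blood was given before V3, the fall may no longer be visible.

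5. **Is an earlier count required anywhere?** No. Section 12 provides for laboratory studies where necessary after a serious adverse event, and section 9 allows unscheduled visits. Neither requires a hemoglobin in the first 24 hours. The section 12 provision applies once an event is already serious, although for bleeding it is the grade that makes it so.

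**The case against.** The strongest reply is that bleeds are not found by routine blood counts. The section 2 rule applies once bleeding is present. Visit 2 has a scheduled bleeding assessment, vital signs half-hourly for six hours and then hourly to 24 hours, and care in a neurological intensive care unit. Nothing forbids a count prompted by a bleed. Section 10 directs treatment of severe bleeding with no hemoglobin criterion. The named safety endpoints in section 12 are mortality and hemorrhagic transformation; non-cerebral bleeding enters only through the adverse event counts. The missing count applies to both arms alike.

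Most of this stands, and it limits the point. A reader might infer that early bleeds will be missed; the documents support only late, undated or unmeasured recognition. A reader might also infer that bleeds will be under-graded, or that the hemoglobin fall is the only objective measure of a bleed. Neither is shown. The documents do not give the GUSTO or TIMI thresholds, imaging is scheduled at 24 hours, and every bleed must be classified on both scales.

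Two parts of the reply do not close the gap. Clinical observation and vital signs do not measure a hemoglobin change, and section 3 itself warns of internal bleeding from latent sources. And although the scheduled omission is the same in both arms, the discretionary testing that fills it need not be, because staff know the treatment.

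**Conclusion.** The point holds as a gap in measurement and an inconsistency between sections. Section 2 uses a hemoglobin fall and a 24-hour window, the Visit 2 text relies partly on laboratory data, and Table 5 schedules no hemoglobin at that visit. A first-day fall may be recognized late, left undated, masked by transfusion, or confounded with antithrombotics begun after 24 hours. Any earlier value depends on unblinded staff.

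No numerical size can be given. A reader might apply the infarction monitoring rates in section 2: major non-cerebral bleeding 3.7% and transfusion 1.6%, so 168 × 0.037 = 6.2 and 168 × 0.016 = 2.7 patients per arm. If one or two of six major bleeds were missed, the rate would be understated by 1/6 = 17% to 2/6 = 33%. The documents do not support this. Section 2 describes the infarction experience as under simultaneous anticoagulant and dual antithrombotic therapy, which section 10 prohibits in the first 24 hours here. Section 2 also gives different doses for infarction and stroke. No share of bleeds in the first day is reported, and the number missed would be invented.

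The primary efficacy analysis and the mortality and hemorrhagic transformation endpoints are not affected. This is a worthwhile, inexpensive improvement to the bleeding data, not a flaw that threatens the trial's main conclusion. It assumes that Table 5 and the visit lists are the complete test schedule; the national guideline cited for Visit 2 care is not in the documents and might call for further tests.

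**What to change.** Reconcile section 2, Table 5 and the Visit 2 text. In Table 5 and the Visit 2 list, add a complete blood count to the coagulogram draw already scheduled, and set that draw at the same time after dosing in both arms. The present text says only that it falls within 24 hours.

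On the CRF, record the lowest available hemoglobin before any transfusion and its change from V1. This value should support the GUSTO and TIMI classification required by section 12, not replace it.

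The cost is one more local laboratory result per patient, on blood already being drawn, and one more CRF field. The change concerns measurement only; it proposes no transfusion threshold or other treatment rule.

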3. POTENTIAL BENEFITS AND RISKS TO PARTICIPANTS

The expected benefit of using the drug is to restore normal blood circulation in the ischemic areas of the brain, which will normalize brain functions and avoid further disability of patients.

The possible undesirable effects of Fortelyzin® is the likelihood of bleeding. Local bleeding (injection sites, oral cavity), as a rule, does not require additional treatment.

Internal bleeding may be caused by latent forms of peptic ulcer, esophageal erosion, bleeding from hemorrhoidal veins, esophageal veins, etc. Thus, careful history taking with special attention to the above-mentioned diseases and a clear selection of patients taking into account all contraindications allows, in most cases, to minimize the risk of bleeding.

During thrombolytic therapy in patients with ischemic stroke, hemorrhagic transformation of the focus is possible. However, it is believed that the benefit of using drugs of this group in patients with thrombosis significantly exceeds the risk of bleeding.

During the study, all adverse events will be carefully controlled. If they appear, all available data will be evaluated and appropriate measures will be taken by the staff of the research centers.

All participants in this clinical study are insured. If a patient is harmed in the trial and this harm is a direct result of the action of the study drug and/or medical manipulations used in accordance with the Study Protocol, the Insurance Company undertakes to fully reimburse the participant all expenses for the necessary medical care.

4. REGULATORY FRAMEWORK AND ETHICAL ASPECTS OF THE STUDY

The clinical trial is conducted in accordance with the guidelines of the International Conference on Harmonization Good Clinical Practice (ICH GCP), the ethical principles set out in the World Medical Association Declaration of Helsinki "Recommendations guiding physicians in biomedical research involving human subjects" (1964-2008), the Directive 2001/20/EC of the European Parliament and the requirements of the legislation of the Russian Federation:

- Federal Law No. 61-FZ "On Circulation of Medicines" (as amended of October 11, 2010);
- Federal Law No. 323-FZ of November 21, 2011 "On the fundamentals of health protection in the Russian Federation" (as amended of July 2, 2013);
- ICH Harmonized Tripartite Guidelines for Good Clinical Practice, 1996
- Rules for quality clinical trials in the Russian Federation (OST 42-511-99);
- Rules of clinical practice in the Russian Federation (2003);
- National Standard of the Russian Federation GOST R 52379-2005 "Good Clinical Practice" (approved by the order of the Federal Technical Regulation and Metrology Agency (Rosstandart) No. 232-ST of September 27, 2005);
- RF Government Regulation of September 13, 2010, No. 714 "On the approval of model rules for Compulsory Insurance of Life and Health of a patient involved in clinical trials of a medicinal product" (as amended by the RF Government No. 393 of May 18, 2011);
- Order of the Ministry of Health and Social Development of the Russian Federation No. 774 of August 31, 2010 "On Ethics Board";
- Guideline for quality clinical trials of medicinal products. Edited by A. N. Mironov, Moscow, 2012;
- RF Government Resolution No. 1012 of December 27, 2007, and No. 186 of March 2, 2009;

- Order of the Ministry of Health and Social Development of the Russian Federation No. 389n of July 6, 2009 "On Approval of Medical Care Procedure to patients with Acute disorders of Cerebral Circulation";
- Order of the Ministry of Health of the Russian Federation No. 928n of November 15, 2012 "On Approval of Medical Care Procedure to patients with Acute disorders of Cerebral Circulation";
- Russian clinical guidelines for thrombolytic therapy in ischemic stroke, developed by the Russian Society of Neurologists and the National Stroke Association (Principal Investigator – Academician of RAS [name] and corresponding member of RAS V. I. Skvortsova), 2012;
- Methodological guide "Thrombolytic therapy in ischemic stroke", of the Ministry of Health and Social Development of the Russian Federation, edited by a corresponding member of RAS V. I. Skvortsova, Moscow, 2010;
- Recommendations for thrombolytic therapy in patients with ischemic stroke. Moscow, 2014;
- Guidelines for the Early Management of Patients with Acute Ischemic Stroke: A Guideline for Healthcare Professionals from the American Heart Association/American Stroke Association. Stroke, 2013; 44: 870-947.

The trial will be initiated in all research centers only after receiving the written permission to conduct the study, approval of the Ethics Committee, and receiving signatures on the clinical trial protocol of each of the parties involved in the study.

Researchers will be timely familiarized with the materials of the study before it begins. The qualification of researchers will meet the requirements necessary to conduct high-quality clinical trials.

The selection of prospective study participants is made on a volunteers basis.

4.1. Ethics Committee

The materials of the clinical trial (including the protocol, Information Sheet, and materials provided to the patient) will be approved by the Ethics Committee of the

Ministry of Health of the Russian Federation before the start of the study. All amendments to the Protocol and updated versions of the Patient Information Sheet will also be submitted to the Ethics Committee.

The clinical trial will be conducted in accordance with the Protocol approved by the Ethics Committee.

4.2. Patient Information Sheet

Informed consent will be obtained from all prospective study participants before any research procedures are initiated. Prior to this, the Investigator must fully inform a patient about all aspects of clinical research, including its purposes, study procedures, expected risks and benefits of participation, and voluntariness of participation.

The patient must be provided with written information about the study (Information Sheet), approved by the Ethics Committee. The patient's information sheet will contain all information about the planned clinical trial, as well as the terms of confidentiality and the use of the patient's data. The rights, safety, and well-being of the participants will take priority and prevail over the interests of science and society. If necessary, information about the procedure for obtaining informed consent from patients/volunteers can be submitted to the Ethics Committee.

Prior to the patient's participation in the clinical trial, two (2) copies of the Informed Consent Form with the patient's name must be signed and personally dated by the patient or the patient's legal representative, or by a person who conducted the informed consent discussion. One copy of signed and dated written Informed Consent will be provided to the patient, and the other will be kept by the Investigator.

When the patient's condition does not allow him/her to express his/her will and there is no legal representative and the need for treatment is urgent, the question of medical intervention in the interest of the patient and his/her inclusion in the study is resolved by a council of physicians, and if it is not possible – by his/her attending (duty) physician with following notification of the Principal Investigator, officials of the medical institution and the legal representative.

The Patient Information Sheet and Informed Consent Form must be reviewed and approved by the Ethics Committee. The final version of the Study Protocol, Individual Patient Registration Form, information for the patient, and Informed Consent Form must be approved by the Russian Ministry of Health and the Local Ethics Committee (if any) at the Research Center.

All subsequent amendments to the above-mentioned documents will also be submitted for approval to these institutions. In addition, these same institutions will be informed about all adverse events associated or possibly related to the use of the study drug.

The information obtained during the study that may reveal the patient's identity will be kept secret and can only be disclosed within the limits established by law.

